2.0 OBJECTIVES AND SCIENTIFIC AIMS

2.1 Study Objectives

- 2.1.1 To evaluate the efficacy of clarithromycin (Biaxin), lenalidomide (Revlimid), and dexamethasone (Decadron) combination therapy (BiRd), compared to lenalidomide and dexamethasone (Rd) alone as an induction therapy for patients with newly diagnosed, transplant ineligible, previously untreated multiple myeloma (MM).
- 2.1.2 To determine the progression free survival (PFS) of the BiRd regimen compared to Rd.
- 2.1.3 To compare objective response rate (ORR) of BiRd versus Rd.
- 2.1.4 To determine and compare duration of response (DOR), event free survival (EFS), time to progression (TTP), and overall survival (OS) of BiRd versus Rd.
- 2.1.5 To assess safety and drug toxicity in each arm.
- 2.1.6 To determine relative dose intensity for each component of protocol medication prescribed.
- 2.1.7 To evaluate and compare minimal residual disease following therapy of BiRd versus Rd.
- 2.1.8 To determine and compare the PFS2 (time from study entry until 2nd instance of disease progression) of BiRd versus Rd.
- 2.1.9 To assess determine and compare quality of life assessments for BiRd vs Rd.

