4.0 INVESTIGATIONAL PLAN

4.1 Study Design

This phase III study, open-label, randomized study investigating lenalidomide and dexamethasone with and without bixin in subjects with newly diagnosed, previously untreated multiple myeloma. Eligible subjects will be randomized in a 1:1 ratio to receive a regimen consisting of either bixin, lenalidomide, and low dose dexamethasone (BiRd arm), or lenalidomide and low dose dexamethasone (Rd arm). Up to 306 patients will be enrolled.

BiRd Arm

Subjects on the BiRd arm will receive bixin, revlimid, and dexamethasone in 28-day cycles. Dosing is as follows:

- Clarithromycin 500mg PO twice daily on days 1-28 for a 28-day cycle. If a dose of clarithromycin is missed, it should be taken as soon as possible on the same day. If it is missed for the entire day, it should not be made up. Vomited doses will not be made up.
- Lenalidomide 25mg PO daily on days 1-21 of a 28-day cycle for patients with a calculated creatinine clearance of ≥ 60 cc/min. Patients with a calculated creatinine clearance of < 60 cc/min will receive 15 mgs PO daily on days 1-21 of a 28 cycle. If a dose of lenalidomide is missed, it should be taken as soon as possible on the same day. If it is missed for the entire day, it should not be made up. Vomited doses will not be made up.
- Dexamethasone 40mg PO will be given on days 1, 8, 15, 22 of a 28-day cycle. Missed or vomited doses will not be made up. If subject cannot tolerate oral dexamethasone, it will be given intravenously.

Rd Arm

Subjects on the Rd arm will receive revlimid, and dexamethasone in 28-day cycles. Dosing is as follows:

- Lenalidomide 25mg PO daily on days 1-21 of a 28-day cycle for patients with a calculated creatinine clearance of ≥ 60 cc/min. Patients with a calculated clearance of < 60 cc/min will receive 15 mgs PO daily on days 1-21 of a 28 cycle. If a dose of lenalidomide is missed, it should be taken as soon as possible on the same day. If it

is missed for the entire day, it should not be made up. Vomited doses will not be made up.

- Dexamethasone 40mg PO will be given on days 1, 8, 15, 22 of a 28-day cycle. Missed or vomited doses will not be made up. If subject cannot tolerate oral dexamethasone, it will be given intravenously.

Correlative studies: Relative dose intensity: Projected total dose per cycle of each component of assigned drug will be divided by the actual dose received and a ratio will be assessed for each cycle delivered.

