MRD: Minimal residual disease testing will be performed in subjects who achieve complete response. MRD testing may be performed either by flow cytometry or PCR, whichever is more readily available at the study institution.

Subjects will continue their randomized treatment assignment until disease progression or unacceptable toxicity (whichever occurs first). In case toxicity precludes dosing of one agent (i.e dexamethasone, clarithromycin, lenalidomide), treatment regimen will continue with the remaining agents. Subjects unable to receive ALL the components of the assigned treatment arms will be removed from study after reasonable attempts to dose reduce and manage side effects. Subjects with elevations of AST/ALT greater than three times the upper limit of normal, with concomitant elevation of bilirubin 2 times the upper limit of normal, not attributable to disease, should be discontinued from treatment. Subjects can also be removed from study at investigator's discretion, or if they withdraw consent. At completion or early discontinuation of treatment, subjects will be followed for 30 additional days or up to the initiation of subsequent treatment (whichever occurs first), after which they will be off the active treatment phase of the study. Long term follow up for disease status and survival will proceed until the subject has withdrawn consent, is lost to follow up, or has died.

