9.6 Dose Modification

Doses of study medications will be modified for toxicity as listed below in Tables 1, 2a, and 2b. Doses must be adjusted for adverse events deemed related to study drug by the investigator. Doses may be adjusted for adverse events related to study medications not listed below at the discretion of the investigator.

Unless otherwise noted, other drugs in the regimen should be continued when the dosing of one or more drugs is delayed due to toxicity.

During BiRd therapy, if toxicity occurs that would indicate an interruption in treatment, the toxicity should be attributed to one or more drugs in the BiRD regimen and dose modifications instituted as instructed in the “Action” column of the table below based on attribution. During maintenance therapy, if toxicity occurs that would indicate a lenalidomide dose modification, toxicity should be attributed to lenalidomide and dose modifications instituted as instructed in the “Action” column of the table below based on attribution.

Table 1: Dose Reduction Steps:

Lenalidomide Dose Reduction

Starting Dose	Lenalidomide PO 25mg/day on days 1-21 of a 28 day cycle
Dose Level -1	Lenalidomide PO 15mg/day on days 1-21 of a 28 day cycle
Dose Level -2	Lenalidomide PO 10 mg/day on days 1-21 of a 28 day cycle
Dose Level -3	Lenalidomide PO 5 mg/day on days 1-21 of a 28 day cycle
Dose Level -4	Lenalidomide PO 5 mg every other day for on days 1-21 of a 28 day cycle

Dexamethasone Dose Reduction

Starting Dose	40 mg PO on days 1, 8, 15 and 22 of a 28 day cycle
Dose Level -1	20 mg PO on days 1, 8, 15 and 22 of a 28 day cycle
Dose Level -2	8 mg PO on days 1, 8, 15 and 22 of a 28 day cycle
Dose Level -3	8 mg PO on days 1 and 15 of a 28 day cycle
Dose Level -4	4 mg PO on days 1 and 15 of a 28 day cycle

Clarithromycin Dose Reduction

Starting Dose	500 mg BID PO days 1-28 of a 28 day cycle
Dose Level -1	250 mg BID PO days 1-28 of a 28 day cycle

Dose Level -2	250 mg PO daily on days 1-28 of a 28 day cycle
Dose Level -3	250 mg PO daily on days odd days of a 28 day cycle
Dose Level -4	Discontinue drug

Table 2a: RD Dose Modification Instructions

Toxicity	NCI Toxicity Grade	Action

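### Section 4.1 defines relative dose intensity as projected over actual dose, so the value rises as dosing falls and is undefined at zero dose

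*Combined protocol and SAP*

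**What the plan says.** Objective 2.1.6 is "To determine relative dose intensity for each component of protocol medication prescribed". It gives no formula. The formula stands under the correlative studies in Section 4.1: "Projected total dose per cycle of each component of assigned drug will be divided by the actual dose received", after which "a ratio will be assessed for each cycle delivered". The calculation is therefore projected over actual, for each component and each delivered cycle.

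Nothing elsewhere corrects this. Section 2.2 does not list relative dose intensity among the endpoints, and Section 14 does not mention it.

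Two other provisions bear on the zero-dose case. Section 4.1 says that when toxicity rules out one agent, the "treatment regimen will continue with the remaining agents". In Table 1 of Section 9.6, the last clarithromycin reduction step is to stop the drug.

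**The concern.** A dose intensity should rise with the dose delivered. The ratio as written does the opposite: 1 is full dose, and larger values mean less drug. A reader who sees 1.67 would take it for overdosing when it is a 40% reduction. In a comparison of arms, the arm with more dose reduction would show the higher figure. That matters because clarithromycin is the only component that differs between arms, and Section 3.5 notes that it may lengthen corticosteroid exposure. Whether BiRd patients received less dexamethasone or lenalidomide than Rd patients is a question this objective should help answer.

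The second problem is division by zero. A cycle delivered with none of one component has no value under the formula, and the plan has no rule for it. If such values were treated as missing, the component-cycles with the poorest delivery would be the ones left out.

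**Working it through.** The documents state no relative dose intensity value, so there is no figure to reproduce. The check applies the written formula and its inverse to the protocol's own dose steps.

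**Inputs, from Table 1 in Section 9.6**

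- Lenalidomide start, "Lenalidomide PO 25mg/day on days 1-21 of a 28 day cycle": 25 × 21 = 525 mg per cycle.
- Lenalidomide level -1, "Lenalidomide PO 15mg/day on days 1-21 of a 28 day cycle": 15 × 21 = 315 mg.
- Dexamethasone start, "40 mg PO on days 1, 8, 15 and 22 of a 28 day cycle": 40 × 4 = 160 mg.
- Dexamethasone level -1, 20 mg on the same four days: 20 × 4 = 80 mg.
- Dexamethasone level -4, "4 mg PO on days 1 and 15 of a 28 day cycle": 4 × 2 = 8 mg.
- Clarithromycin start, 500 mg twice daily for 28 days: 1,000 × 28 = 28,000 mg.
- Clarithromycin level -1, 250 mg twice daily: 500 × 28 = 14,000 mg.
- Clarithromycin level -3, 250 mg on odd days: 250 × 14 = 3,500 mg.
- Clarithromycin level -4, stopped: 0 mg.

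The projected dose is taken here as the Table 1 starting dose. The direction of the result does not depend on that choice.

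**Results for one cycle**

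| Component and level | As written (projected/actual) | Inverse (actual/projected) |
|---|---|---|
| Any component, full dose | 1.00 | 1.00 |
| Lenalidomide -1 | 525/315 = 1.67 | 315/525 = 0.60 |
| Dexamethasone -1 | 160/80 = 2.00 | 80/160 = 0.50 |
| Dexamethasone -4 | 160/8 = 20.0 | 8/160 = 0.05 |
| Clarithromycin -1 | 28,000/14,000 = 2.00 | 14,000/28,000 = 0.50 |
| Clarithromycin -3 | 28,000/3,500 = 8.00 | 3,500/28,000 = 0.125 |
| Clarithromycin -4 | 28,000/0, undefined | 0/28,000 = 0 |

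**If ratios are averaged (an assumption)**

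The mean of projected/actual is a mean of reciprocals. Turning it over gives the harmonic mean of actual/projected, which is not the arithmetic mean unless all cycles are equal.

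- One full-dose and one half-dose cycle: (1 + 2)/2 = 1.50, reciprocal 0.67. The true mean is (1 + 0.5)/2 = 0.75.
- Nine full-dose dexamethasone cycles and one at level -4: (9 × 1 + 20)/10 = 2.90, reciprocal 0.34. The true mean is (9 × 1 + 0.05)/10 = 0.905. One heavily reduced cycle dominates the summary.

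**The denominator after correction**

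Inverting the formula is not enough, because the protocol gives more than one projected dose.

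- Section 4.1 sets lenalidomide by creatinine clearance. A patient assigned 15 mg who takes every dose scores 315/315 = 1.00 against the assigned dose, but 315/525 = 0.60 against 25 mg.
- The footnotes to the medication schedules in Section 1.1 give 20 mg dexamethasone for an age group, while Section 4.1 gives 40 mg without an age rule. A patient who takes 20 mg weekly scores 80/80 = 1.00 or 80/160 = 0.50.
- Section 9.1 starts lenalidomide on day 3 of cycle 1, and Section 4.1 starts it on day 1. At 25 mg the projected dose is 19 × 25 = 475 mg or 21 × 25 = 525 mg.
- The maintenance regimen in Section 9.1 lists lenalidomide and dexamethasone but no clarithromycin, while Section 4.1 continues the randomized regimen until progression or unacceptable toxicity. If the maintenance list is followed, the projected clarithromycin dose is 0 and actual/projected is 0/0.

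**The case against.** The strongest reply is that little follows from this. The measure is correlative, it is absent from the endpoint list and from Section 14, and no test, alpha, sample size or stopping rule depends on it. Actual doses are recorded through diaries and capsule counts (Section 10.5) and dosing records (Section 7.2.8). Any single non-zero ratio can be inverted exactly, and a programmer could apply the usual formula without loss of information. All of this stands and limits the size of the point. It does not remove it: Section 4.1 is the only definition of a listed objective, and using another formula would depart from the written plan.

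The zero-dose case is also narrower than it first looks. In Table 1 the lowest steps for lenalidomide and dexamethasone are above zero. Every row of Tables 2a and 2b that explicitly discontinues a drug also takes the patient off study. Section 4.1 goes on to remove subjects who cannot receive all the components, which could mean unable to take every one or unable to take any. Zero-dose cycles remain possible under the provision for continuing with the other agents and under the clarithromycin stopping step, but nothing in the documents shows how often they would occur.

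A reader might go further in two ways that the documents do not support. One is to infer that the trial would report a mean of 1.50, or any mean at all: Section 4.1 specifies only per-cycle ratios, and the mixes of cycles used above are illustrations. The other is to infer that patients who stop a drug would vanish from the summary and that poor tolerability would be hidden. Only the zero-dose cycles of that component are undefined; the patient's other cycles and other drugs keep their values. Toxicity frequencies with exact confidence intervals are reported separately under Section 14.4, and event-free survival, which counts regimen intolerance (Section 2.2), is presented there descriptively.

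**Conclusion.** The concern holds as an inverted definition. On the protocol's dose steps, reduced dosing gives values from 1.67 (lenalidomide level -1, for a patient assigned 25 mg) to 20.0 (dexamethasone level -4), where 0.60 and 0.05 are meant. A delivered cycle with zero dose of a component is undefined. These figures rest on the Table 1 starting doses as reference; the inversion itself rests on no assumption. That a summary could not be converted back depends on averaging, which the plan does not state.

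The effect is confined to a correlative, descriptive measure. The primary PFS comparison is untouched. The definition should be corrected, but it does not threaten the trial's main conclusion.

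**What to change.** Replace the formula in Section 4.1 with a definition along these lines:

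- For each component and each delivered cycle, relative dose intensity is the total dose received divided by the total dose projected.
- The projected dose is the starting dose that the protocol assigns to that patient in that treatment phase. It is not the reduced dose in force, because that would make dose reductions invisible.
- A component projected for the cycle but not given scores 0.
- Where the protocol projects no dose of a component, no ratio is computed, so that an omission the protocol itself specifies is not scored as poor delivery.

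Reconcile the passages that set the projected dose: the creatinine-clearance rule in Section 4.1, the age footnotes in Section 1.1, the cycle 1 lenalidomide start day in Section 9.1 against Section 4.1, and the maintenance regimen in Section 9.1. Which dosing text should stand is for the sponsor and investigators to settle; the analysis needs only one projected dose per patient, component and cycle. It would help to name the summary to be reported at the same time.

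The cost is a short text edit plus that reconciliation, so somewhat more than one sentence. No new data collection is needed.

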Due to the potential increased risk of developing secondary primary malignancies associated with lenalidomide treatment, patients will be advised to undergo regular cancer screenings as part of standard of care. Monitoring for development of acute leukemia and Hodgkin's lymphoma will be performed by review of regular blood work, chemistry panel, and LDH at each visit including during follow-up. Particular attention will be paid to the complete blood count differential with a low threshold to investigate emerging cytopenias or altered differential with either bone marrow biopsy or PET scanning if clinically indicated. In addition, men and women will be advised to have a yearly skin exam by a dermatologist and regular colonoscopy screening (every 5 years or earlier, depending on GI recommendations). Women will also be advised to have yearly mammograms and regular cervical cancer screening. Men will also be advised to undergo yearly Prostate-Specific Antigen (PSA) testing.

For information on the risk of venous thromboembolism with combined oral contraception see **Appendix III: Risks of Fetal Exposure, Pregnancy Testing Guidelines and Acceptable Birth Control Methods.**

Cycles will be repeated every 28 days. Patient will return to clinic every 28 days for evaluation of toxicity and response and will remain on study until progression of disease, toxicities become excessive, or until discontinuation for another reason (see Section 9.2). Doses may be modified due to side effects.

Patients who achieve a resolution of monoclonal gammopathy as detected on serum immunofixation or achieve a plateau of disease (no change in quantitative M-spike or free light chains) for > 2 cycles will be transitioned to maintenance therapy. Maintenance therapy will consist of dexamethasone at a dose of 20mg weekly (given on days 1, 8, 15, and 22 of a 28 day cycle) and lenalidomide at a dose of 25 mg/day on days 1-21 of a 28 day cycle (a dose of 15mg/day days 1-21 of a 28 day cycle will be given to patients with a creatinine clearance of < 60 cc/min).

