9.5 Instruction for initiation of a new cycle

A new course of treatment may begin on the scheduled Day 1 of a new cycle if:

- Absolute neutrophil count (ANC) ≥ 750 cells/mm³
- Platelets count $\geq 50,000$ /mm³
- Any other drug-related adverse events that may have occurred have resolved to \leq grade 2 severity.

If these conditions are not met on Day 1 of a new cycle, the subject will be evaluated weekly and a new cycle of treatment will not be initiated until the toxicity has resolved as described above. If the toxicity does not resolve within four weeks, the patient will be taken off the study. If the dosing of clarithromycin, lenalidomide or dexamethasone was halted during the previous cycle and was restarted with a one-level dose reduction without requiring an interruption for the remainder of the cycle, then that reduced dose will be initiated on Day 1 of the new cycle. If the dosing of clarithromycin, lenalidomide or dexamethasone was omitted for the remainder of the previous cycle or if the new cycle is delayed due to toxicity newly encountered on the scheduled Day 1, then the new cycle will be started with dose modifications as described in Section 9.6 and Table 2.

If the start of a new cycle is delayed more than 4 weeks, the patient will be removed from the protocol.

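### Relative dose intensity in section 4.1 has no time term, so the cycle delays of up to 4 weeks that sections 9.4 and 9.5 allow are not counted and delivered intensity is overstated

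*Combined protocol and SAP*

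**What the plan says.** Section 2.1 lists the objective: "To determine relative dose intensity for each component of protocol medication prescribed". Section 4.1 (Correlative studies) gives the only formula: "Projected total dose per cycle of each component of assigned drug will be divided by the actual dose received". The unit of assessment is the cycle actually given, since the same sentence ends by saying that "a ratio will be assessed for each cycle delivered". There is no time term and no cumulative summary per patient. Section 2.2 does not list dose intensity among the endpoints, and section 14 does not mention it.

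The planned cycle is fixed in section 9.1: "Cycles will be repeated every 28 days". Under section 9.5 a new cycle waits until neutrophils, platelets and other drug-related events meet the Day 1 criteria, with weekly re-evaluation. The limit is: "If the start of a new cycle is delayed more than 4 weeks, the patient will be removed from the protocol". Section 9.4 sets the same limit.

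Section 9.5 also says that a cycle delayed by toxicity newly found on Day 1 restarts with the dose modifications of section 9.6 and its tables. Section 9.6 says that, unless otherwise noted, the remaining drugs carry on when one or more is delayed for toxicity.

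**The concern.** Dose intensity is dose per unit of time. A ratio of doses within a cycle, calculated only for cycles given, measures something narrower: how completely each started cycle was taken. Holds and reductions inside a cycle lower the dose received and so affect the ratio. Time lost before the next cycle starts does not.

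What is at stake is the description of how much drug each arm received. Readers will use RDI to judge whether adding clarithromycin changed delivery of the lenalidomide and dexamethasone backbone. If one arm had more or longer delays, the section 4.1 measure would not show it.

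**Working it through.** The documents give no RDI value, so there is no figure to reproduce.

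**Inputs**
- Lenalidomide (4.1): "Lenalidomide 25mg PO daily on days 1-21 of a 28-day cycle", for creatinine clearance of at least 60 cc/min. 25 × 21 = 525 mg per cycle, or 525/28 = 18.75 mg/day.
- Dexamethasone (4.1): "Dexamethasone 40mg PO will be given on days 1, 8, 15, 22 of a 28-day cycle". 40 × 4 = 160 mg per cycle.
- Clarithromycin (4.1): "Clarithromycin 500mg PO twice daily on days 1-28 for a 28-day cycle". 1,000 × 28 = 28,000 mg per cycle.
- Planned cycle 28 days (9.1); longest delay without removal 4 weeks (9.4, 9.5).

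These doses are used only for illustration. The planned dose cancels, so the ratios below are the same for any dose level.

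**One interval, Day 1 to next Day 1.** Assume the cycle is taken in full and nothing is taken in the gap.

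Section 4.1 score = projected / received = 525/525 = 160/160 = 28,000/28,000 = 1.00.

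Time-based RDI = (dose / (28+7w)) / (dose / 28) = 28/(28+7w).

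| Delay | Time-based RDI | 4.1 score | Overstatement (28+7w)/28 |
|---|---|---|---|
| 0 | 1.00 | 1.00 | 1.00 |
| 1 week | 28/35 = 0.80 | 1.00 | 1.25 |
| 2 weeks | 28/42 = 0.667 | 1.00 | 1.50 |
| 3 weeks | 28/49 = 0.571 | 1.00 | 1.75 |
| 4 weeks | 28/56 = 0.50 | 1.00 | 2.00 |

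For lenalidomide with a 4-week delay: 525/56 = 9.375 mg/day against 18.75 planned.

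**A whole course**, first dose to the end of the last 28-day cycle, n cycles:
- One 28-day delay: 28n/(28n+28). Six cycles, 168/196 = 0.857; twelve cycles, 336/364 = 0.923.
- Three 28-day delays in twelve cycles: 336/420 = 0.80.
- Every gap at the maximum: n/(2n−1). This is 0.667 for 2 cycles, 0.545 for 6, 0.522 for 12 and 0.511 for 24. It approaches 0.50 but does not reach it.

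The 4.1 score is 1.00 per cycle in all of these.

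**Delay together with a reduction.** Suppose lenalidomide goes from 25 to 15 mg (Table 1, first step) after a 4-week delay, and the reduced dose is counted over a 56-day interval. Received over projected starting dose is 315/525 = 0.60. The time-based value is (315/56)/(525/28) = 0.30. The reduction is seen and the delay is not. If projected means the modified dose, which section 4.1 does not settle, the score is 315/315 = 1.00 and neither is seen.

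**When a full score can follow a delay.** In Tables 2a and 2b the neutropenia and thrombocytopenia rows act on lenalidomide only (the latter also on anticoagulation), so dexamethasone and clarithromycin can restart at full dose. The neutropenia rows let lenalidomide be maintained with G-CSF.

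**The case against.** The strongest reply is that the protocol seldom pairs a toxicity delay with full dosing of the responsible drug. Section 9.5 restarts such a cycle with dose modifications, so if projected means the starting dose the ratio already leaves 1.00. That stands, and it limits how often a full score follows a delay for the drug held responsible. It does not recover the lost time, and it does not apply to drugs not held responsible.

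Second, section 9.6 has other drugs continue when one is delayed. If that covers the gap between cycles, those drugs lose less intensity than the table shows. The documents do not say how it fits with section 9.5, which does not start a new cycle until toxicity resolves, nor how doses taken in the gap would be credited. The table's assumption of no dosing in the gap is therefore an upper bound on the effect for those drugs.

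Third, a reader might infer that delay is one of the protocol's two main responses to toxicity. Tables 2a and 2b do not support this: most rows hold, reduce or discontinue a drug, and within-cycle holds are captured by the ratio. Delay applies only when the Day 1 criteria fail.

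Fourth, no planned inference rests on RDI. It is a correlative measure, objective 2.1.6 says determine rather than compare, and the primary PFS comparison is by intention to treat. This stands.

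**Conclusion.** The section 4.1 rule does not measure dose intensity, because it ignores time between cycles. For each delayed interval it overstates delivered intensity by (28+7w)/28, from 1.25 to 2.0, if the drug is not taken in the gap. Over a course the effect is smaller and depends on how many cycles are delayed, which the documents do not predict.

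Two stronger readings are not supported. One is that a patient treated at half the planned intensity throughout would score full. Half is exact only for a single 56-day interval; over a course it is a limit that would need every gap at the 4-week maximum. The other is that the arms will look equally dosed when Rd received more backbone drug, which would confuse the PFS and toxicity comparison. Nothing in the documents shows that delays will differ by arm, and PFS is analysed regardless of compliance.

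Separately, the ratio as written puts projected dose over received dose, so half a dose scores 525/262.5 = 2.0 and a cycle with none taken is undefined. Turning it over would not reveal delays, but both faults should be mended together. This is a worthwhile correction to a descriptive measure.

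**What to change.** In section 4.1, define RDI per patient and per drug as:

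(cumulative dose actually received / actual days from first dose to the end of the last cycle, delays included) ÷ (cumulative planned dose for the cycles started / (28 × number of those cycles)).

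- State that planned dose means the protocol starting dose for the assigned arm, renal function, age group and treatment phase, before any toxicity reduction.
- Count any doses taken during a delay, and state how the end of the last cycle is set when treatment stops part-way.
- Tabulate the number and length of cycle delays by arm. The per-cycle ratio, as received over planned, can be kept as a separate display.

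Fixing the planned dose requires reconciling passages that disagree: the dexamethasone dose by age in the section 1.1 schedules against sections 4.1 and 9.1; the first lenalidomide day of cycle 1 in 4.1 against 9.1; and the clarithromycin frequency in 4.1 against the instruction line of the Appendix VIII diary.

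The cost is a change of wording and one extra derivation from Day 1 dates, drug diaries and capsule counts (sections 1.3, 7.2.8 and 10.5). No new data and no change to treatment are needed. Reported RDI will be somewhat lower.
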